**Programming Hints for assignment of fatalities applicable to all exposure strategy (see also Section 9.3.2):**

- For mortality events: the fatal SAE onset date should be used as the 'Event Date' when slotting the death to the relevant analysis time period, and as a result corresponding exposure group. In the case of multiple fatal SAEs, the latest onset date should be used.
- For individual's subject-years at-risk computation, the date of death should be used as the 'Event Date'.

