8.3.2 Analysis of Primary Endpoints

In addition to analyses that consider initial treatment group (BENLYSTA cohort vs. comparison cohort), analyses that specifically account for changes in therapy (in either group) by considering a variety of risk windows will be employed. These analyses will attribute events to BENLYSTA treatment if they occur within the designated risk windows for BENLYSTA exposure and to comparison treatment otherwise. These analyses will allow for a registry patient to contribute person-time to both BENLYSTA treatment, and comparison treatment and as a result, will specifically account for treatment switching to BENLYSTA or from BENLYSTA. Switching between BENLYSTA and comparison treatment will be taken into account in a number of ways in the analysis and will be further defined within the statistical analysis plan. No new analyses for changing between BENLYSTA formulation or stratifying by BENLYSTA formulation are planned. Planned analyses are outlined below; all analyses will be detailed in the statistical analysis plan.

- Analysis by initial treatment group of rate per person years of observation time.
- Analysis by initial treatment group of rate per person years of exposure where BENLYSTA exposure ends 14 weeks (approximately 5 half-lives) after cessation of treatment.
- For serious psychiatric events, BENLYSTA exposure is all time on treatment with BENLYSTA ending 14 weeks (approximately 5 half-lives) after cessation of treatment, with all remaining treatment time attributed to the comparison cohort.
- For serious infections, opportunistic infections and other infections of interest, BENLYSTA exposure is all time on treatment with BENLYSTA ending 6 months after cessation of treatment, with all remaining treatment time attributed to the comparison cohort.
- For NMSC and malignancies excluding NMSC, analysis will be performed where all events will be attributed to BENLYSTA if the patient was ever exposed to BENLYSTA treatment prior to the event and attributed to the comparison cohort otherwise (ie, once exposed, always at risk).
- Mortality will be analyzed applying all the above-mentioned risk windows (eg, 14 weeks, 6 months, and ever-exposed).
- Other risk windows (including risk windows for comparison treatment) may also be assessed and defined in the statistical analysis plan.

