***Benlysta End Date*** + 98 days or 183 days when switching from Benlysta to Non-Benlysta (i.e. Exposed to Unexposed) period. *Period with this end date will be assigned 'Benlysta' or 'Exposed' group.*

***Next Benlysta Start Date*** – 1 when switching from Non-Benlysta to Benlysta (i.e. Unexposed to Exposed) period. *Period with this end date will be assigned 'Non-Benlysta' or 'Unexposed' cohort*
  - For last or final exposure period, ***Period End Date*** is the ***Last Contact Date***\*

- Identify or map events experienced during the study to the specific exposure period satisfying:

Follow-up Period Start Date ≤ Event Onset Date ≤ Follow-up Period End Date

NOTE: for incidence rate calculation, first event is retained for each exposure group (i.e. Benlysta and Non-Benlysta).

- Calculate individual's subject-years of follow-up for time spent in each exposure group *j* (where *j* =1(Exposed), 2(Unexposed)) as follows:

- For overall or 60-Month+ time period, calculate ‘*period follow-up time*’ (*pFUt*) in days for each period  $i$  ( $i=1, 2, \dots, n$ ) as:
  - (Period End Date – Period Start Date) +1
- For other xx-Month time periods ( $xx = 12, 24, 36, 48$ ), calculate ‘*period follow-up time*’ (*pFUt*) in days as follows:
  - Calculate cumulative follow-up duration for each exposure period  $i$  (CM\_FUD[ $i$ ])
  - Identifying qualifying exposure period for each xx-Month time specific computation as period where previous CM\_FUD value is less than xx-Month target visit day (i.e.  $CM\_FUD[i-1] < xx\text{-Month target visit day}$  for  $i=1, 2, \dots, n$ ; where  $CM\_FUD[0] = 0$ )
  - For each qualifying exposure period for xx-Month time, calculate xx-M\_pFUt =
    - $CM\_FUD[i] - CM\_FUD[i-1]$  if  $CM\_FUD[i] \leq xx\text{-Month target visit day}$
    - $xx\text{-Month target visit day} - CM\_FUD[i-1]$  if  $CM\_FUD[i] > xx\text{-Month target visit day}$
    - where  $CM\_FUD[0] = 0$
- Calculate each individual subject-year of follow-up (*syFUj*) as follows:
  - For each exposure group  $j$  ( $j=1$ (Exposed),  $2$ (Unexposed)), sum *pFUt* over all periods  $i$  with the same exposure group and divided by 365.25
    - $syFU_j = (\sum_{i=1}^n pFU_{t_{i(j)}}) / 365.25$  (for overall or 60+Month time period)
    - $xxM\_syFU_j = (\sum_{i=1}^n xxM\_pFU_{t_{i(j)}}) / 365.25$  (for time period specific computation)

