(NOTE: For time period analysis, the above computation will be done for the following time periods: 12-month, 24-month, 36-Month, and 48-Month).

- Individual’s subject-years ‘at-risk’ (*syARj*) will be calculated for each exposure group  $j$  ( $j = 1$ (Exposed),  $2$ (Unexposed)) as follows:
  - Calculate *period ‘at-risk’ time* (*pARTi*) for each exposure period  $i$  ( $i=1, 2, \dots, n$ ) or qualifying exposure period for xx-Month time as:
    - if no event occurred in the exposure period (for overall or 60-Month+ time period calculation) or event day  $> xx\text{-Month target visit day}$  (for xx-Month time period specific calculation)
      - $pART_i = \text{‘period follow-up time’ (pFUt) or}$

$$xxM\_pARt_i = xxM\_pFUt \text{ (for time specific calculation)}$$

- for period where first event occurred (per exposure group) or event day  $\leq$  xx-Month target visit day

$$pARt_i = event\ day - CM\_FUD[i-1]$$

$$xxM\_pARt_i = event\ day - CM\_FUD[i-1] \text{ (in case of time specific calculation)}$$

$$\text{where } CM\_FUD[0] = 0$$

- o For each exposure group  $j$  ( $j=1$ (Exposed),  $2$ (Unexposed)) separately compute individual subject-year at-risk  $syAR_j$  thus:

- For subjects with no events in exposure group  $j$ , sum  $pARt_i$  for all periods  $i(j)$  (i.e. periods occurring while on exposure group  $j$ )

$$syAR_j = (\sum_{i=1}^n pARt_{i(j)})/365.25$$

$$xxM\_syAR_j = (\sum_{i=1}^n xxM\_pARt_{i(j)})/365.25 \text{ (for time period specific computation)}$$

- For subjects with at least one event in exposure group  $j$ , sum  $pARt_i$  for all periods  $i(j)$  up to period where the first event in exposure group  $j$  occurred

$$syAR_j = (\sum_{i=1}^{n^*} pARt_{i(j)})/365.25$$

$$xxM\_syFU_j = (\sum_{i=1}^{n^*} xxM\_pFUt_{i(j)})/365.25 \text{ (for time period specific computation)}$$

where  $n^*$  is the period where the first event was experienced  
(NOTE: Time spent in subsequent exposure periods for the same exposure group after an event had occurred will not be counted)

**NOTE:** Individual's subject-years at-risk will be calculated for each event category separately

\* Last Contact Date as defined in Section 9.5.3

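### Mortality uses fatal-SAE onset to place a death but date of death to end its at-risk time, so deaths and person-time can fall in different groups or periods

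*SAP*

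**What the plan says.** SAP 9.2.1 has a short block headed "Programming Hints for assignment of fatalities applicable to all exposure strategy". It sets two dates for the same event:

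- **Placement.** For mortality, "the fatal SAE onset date should be used as the 'Event Date' when slotting the death to the relevant analysis time period"; the exposure group follows from this. "In the case of multiple fatal SAEs, the latest onset date should be used", so placement is always by an onset date.
- **Person-time.** "For individual's subject-years at-risk computation, the date of death should be used as the 'Event Date".

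The strategies then use these dates as follows.

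- **While On Initial Exposure (SAP 9.2.1.1).** An event counts if its date is before the first switch date. At-risk time ends at the earliest of event, first switch and last contact. SAP 5.1 lists this strategy under primary analysis, and SAP 7.3 carries it into the weighted rates.
- **As-Exposed (SAP 9.2.1.2).** Events are mapped by "Follow-up Period Start Date ≤ Event Onset Date ≤ Follow-up Period End Date". At-risk time in the event period is the event day minus cumulative follow-up before that period, with no cap at the period's end. A group with no mapped event contributes all its time. SAP 5.1 calls this strategy exploratory.
- **Ever-Exposed (SAP 9.2.1.3).** Exploratory. Unexposed at-risk time is capped at the BENLYSTA start date.
- **Last contact (SAP 9.5.3).** For a patient who dies, this is the date of death.

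The SAP gives no rule for a switch or period boundary between onset and death. The limitations it lists for its strategies do not mention the point.

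**The concern.** A mortality rate should be deaths divided by the person-time in which those deaths could have been counted. With two dates, the numerator follows one clock and the denominator another. Whenever a switch or a time-period boundary lies between onset and death, the death is credited to one group or period while the last stretch of life is credited to another, or to none.

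Mortality is a primary endpoint, and one affected strategy, While On Initial Exposure, is a primary analysis. Deaths are few, so moving a handful can change a between-group comparison by an amount similar to the planned precision. The bias can run either way: onset on BENLYSTA with death after the window adds a death to BENLYSTA, and onset before BENLYSTA starts with death afterwards takes one away.

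**Working it through.** **Inputs.** Mortality 0.68 per 100 patient-years in both groups, 10% annual drop-out, and 2,000 and 1,000 patients (protocol 8.2); windows of 98 and 183 days (SAP 9.2.1.2); Month 12 target Day 366 (SAP 5.3).

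**The plan's own figures.** Person-years = N × (1 − 0.9⁵)/(−ln 0.9), giving 7,773.5 and 3,886.8, as stated. The half-width of the rate difference is 1.96 × √[0.0068 × (1/7,773 + 1/3,886)] = 0.0032 per patient-year, or 0.3175 per 100, which matches the ±0.32 in protocol Table 8-1.

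**The formulas applied to hypothetical deaths.**

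- Case A: BENLYSTA stops Day 300, switch Day 398 (300 + 98), onset Day 350, death Day 450.
- Case B: Non-BENLYSTA at enrollment, onset Day 390, BENLYSTA starts Day 401, death Day 460.
- Case C: onset Day 300, BENLYSTA stops Day 310, switch Day 408, death Day 900.

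For As-Exposed there are two readings. In reading 1, onset selects the event period and the date of death fills it. In reading 2, the date of death also selects the period for the at-risk calculation.

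| Case and strategy | Death counted in | BENLYSTA days | Non-BENLYSTA days | Sum / days lived |
|---|---|---|---|---|
| A, As-Exposed, reading 1 | BENLYSTA | 450 − 0 = 450 | 450 − 399 + 1 = 52 | 502 / 450 |
| A, As-Exposed, reading 2 | BENLYSTA | 398 | 52 | 450 / 450 |
| A, While On Initial Exposure | BENLYSTA | min(450, 398) = 398 | none | 398 / 450 |
| B, As-Exposed, reading 1 | Non-BENLYSTA | 60 | 460 | 520 / 460 |
| B, As-Exposed, reading 2 | Non-BENLYSTA | 60 | 400 | 460 / 460 |
| B, Ever-Exposed | Non-BENLYSTA | 460 − 401 + 1 = 60 | min(460, 401) − 1 = 400 | 460 / 460 |
| C, As-Exposed, reading 1 | BENLYSTA | 900 | 900 − 409 + 1 = 492 | 1,392 / 900 |
| C, As-Exposed, reading 2 | BENLYSTA | 408 | 492 | 900 / 900 |

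In every row the death is placed in a group whose own time had ended when the patient died. Days count twice only in As-Exposed under reading 1. In case A under While On Initial Exposure, onset (Day 350) precedes the switch, so the death counts, although it occurs 52 days after at-risk time stopped. With the 183-day window, case A has no switch before death (300 + 183 = 483) and no mismatch.

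**By time period.** With onset in Month 11 and death in Month 30, onset precedes Day 366, so this is a 12-month death. Twelve-month person-time stops at Day 366 with the patient alive.

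**Overall ITT.** One group, no switch rule, and at-risk time to death: no mismatch.

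**Size of the double count (reading 1 only).** Expected deaths are 0.0068 × 7,773 = 52.9 and 0.0068 × 3,886 = 26.4. Assume 5-20% of the 52.9 (2.6 to 10.6 deaths) have a switch between onset and death.

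- Switch 14-180 days before death: from 2.6 × 14/365.25 = 0.1 to 10.6 × 180/365.25 = 5.2 patient-years.
- Interval as long as in case C: 3 × 492/365.25 = 4.0 to 11 × 492/365.25 = 14.8 patient-years. Even this is below 0.4% of either planned total (14.8/3,886 = 0.38%).

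**Size of the placement effect (As-Exposed, planned person-years held fixed).** Placing the same deaths by date of death gives:

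| Share assumed | Deaths moved | BENLYSTA rate per 100 | Non-BENLYSTA rate per 100 | Difference |
|---|---|---|---|---|
| 5% | 2.6 | (52.9 − 2.6)/77.73 = 0.65 | (26.4 + 2.6)/38.86 = 0.75 | 0.10 |
| 20% | 10.6 | (52.9 − 10.6)/77.73 = 0.54 | (26.4 + 10.6)/38.86 = 0.95 | 0.41 |

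In While On Initial Exposure such deaths would leave the BENLYSTA numerator and not move to the other group.

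**The case against.** The strongest defence is that attribution by onset is right for safety. A fatal illness that begins on BENLYSTA and leads to stopping should not be charged to the comparison group because the patient died after the window closed. SAP 9.2.1.2 maps events by onset generally, and protocol 7.1 treats death as an outcome of an adverse event. This stands as a reason to keep an onset analysis. It does not explain why the denominator uses another date.

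Several stronger inferences are tempting, but the documents do not support them.

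- **That mortality person-time is counted twice as a matter of course.** The event-period branch, "for period where first event occurred (per exposure group) or event day", does not say which date selects the period. If the date of death is used throughout the at-risk calculation, no day counts twice. Ever-Exposed caps unexposed time, and ITT and While On Initial Exposure keep one group per patient.
- **That the SAP contradicts the protocol.** Protocol 8.3.2 says "These analyses will attribute events to BENLYSTA treatment if they occur within the designated risk windows for BENLYSTA exposure and to comparison treatment otherwise". It does not define the event date for mortality, and it leaves the handling of switching to the SAP.
- **That the risk windows become unbounded.** SAP 5.3 excludes events after 63 months, and the latest-onset rule for multiple fatal SAEs shortens the interval.
- **That deaths whose cause began before enrollment drop out of every strategy.** Protocol 7.2.1 records AESI from enrollment, and protocol 7.1 counts worsening of a pre-existing condition as an adverse event. Nothing shows fatal SAEs recorded with earlier onsets. This justifies a safeguard only.

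**Conclusion.** The point holds. SAP 9.2.1 sets two Event Dates for one death, and a switch or period boundary between them separates the death from its person-time. This affects While On Initial Exposure (primary), As-Exposed, Ever-Exposed and the by-time-period tables; overall ITT mortality is essentially unaffected.

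The double count is minor: about 0.1 to 15 patient-years under the assumptions shown, in an exploratory analysis, on one of two readings. Placement of the death matters more. About 3-11 deaths would change group in As-Exposed, for a rate difference of 0.10 to 0.41 per 100 patient-years against a planned precision of ±0.32. That range rests on an assumed 5-20% share with no basis in the documents, on the planning rate, on person-years that ignore crossover, and on crossings in one direction only. It shows what the rule could do and does not predict the result.

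**What to change.** In SAP 9.2.1:

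1. Within each mortality table, use one Event Date for slotting, exposure group, time period and at-risk time.
2. Report mortality both ways: by date of death, with at-risk time ending at death; and by fatal-SAE onset, with at-risk time ending at onset and later time credited to neither group.
3. Label which version is main. If onset is kept as main, state that attribution by onset is intended.
4. Cap at-risk time in any As-Exposed period at that period's end date.
5. In the overall ITT analysis, count every on-study death whatever the recorded onset date of its cause.

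The cost is a few sentences and one extra mortality run, with no new data. In the date-of-death version, deaths from an illness that began on BENLYSTA move to Non-BENLYSTA in As-Exposed, or leave the While On Initial Exposure numerator, when the switch precedes death. The onset version shows those deaths, which is the reason to report both.

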#### 9.2.1.1. Initial Exposure

This is defined as subjects' exposure arm assignment (Benlysta or Non-Benlysta) at the time of enrollment (Baseline). Due to potential for one or more treatment switching during the follow-up, two different analysis approaches will be used for 'Initial Exposure' strategy; namely, 'ITT' and 'While On Initial Exposure'.

1. ITT approach will use all accrued data during the whole follow-up period irrespective of treatment switching. Subjects entering the study on Benlysta medication will be considered 'Exposed' and those on Non-Benlysta SLE medications are considered 'Unexposed' throughout the study period.

A limitation of the ITT is potential bias from mismatch of events to exposure arm since events occurring after exposure switching are attributed to that Initial Exposure. This will attribute events to Benlysta exposure when subjects are no longer exposed and vice-versa (i.e. Non-Benlysta initial cohort switched to Benlysta). See Section 9.2.1.2 for details of 'As-Exposed' (Time Varying) approach to address this limitation

**Programming Hints for derivation of essential variables needed for computation of incidence and event rates (presented in Section 7.1.5.1) under the ITT approach:**

- Compute individual's subject-years at-risk as:  

$$\frac{[(\text{minimum}(\text{Event Date}, \text{Last Contact Date}^*) - \text{Study Enrollment Date}) + 1]}{365.25}$$

- Compute individual's subject-years of follow-up as:  

$$[(\text{Last Contact Date}^* - \text{Study Enrollment Date}) + 1] / 365.25$$
- Consider events experienced during the whole study period:  

$$\text{Study Enrollment Date} \leq \text{Event Date} \leq \text{Last Contact Date}^*$$
  - For incidence rate calculation only count new cases (i.e. first onset) of the event experienced during the period
  - For events rate calculation count all the events experienced during the period

## NOTE:

- i. Individual's subject-years at-risk will be calculated for each event type separately and if required for each time period (i.e. for analysis by time period)
- ii. Individual subject-years of follow-up may be required for each time period (i.e. for analysis by time period)

\* Last Contact Date as defined in section 9.5.3

2. While On Initial Exposure analysis approach will be used to analyze all data accrued up to the first treatment switch. Any events and follow-up time accrued after the first exposure switching (switching from Initial Exposure) will be censored (i.e. excluded from analysis) at first exposure switch date (see Section 5.14 for the definition of exposure/medication switching).

A limitation of this analysis approach is potential bias introduced by underreporting of events experienced during the study since data from only a subset of the study period and events collected before the first treatment switch are included in the analysis. The results only present risk of exposure prior to first treatment switch. See Section 9.2.1.2 for details of 'As-Exposed' (Time Varying) approach to address this.

**Programming Hints for derivation of essential variables needed for computation of incidence and events rates (presented in Section 7.1.5.1) under the While On Initial Exposure approach:**

- Compute First Switch Date as:  

$$\text{Baseline Benlysta Medication End Date} + 98 \text{ days (for switching from Benlysta to Non-Benlysta) or}$$

$$\text{First Post-Baseline Benlysta Start Date} - 1 \text{ (for switching from Non-Benlysta to Benlysta)}$$
- Compute individual's subject-years at-risk as:  

$$[(\text{minimum (Event Date, First Switch Date, Last Contact Date}^*) - \text{Study Enrollment Date}) + 1] / 365.25$$

- Compute individual's subject-years of follow-up as:
 
$$\frac{[(\text{minimum}(\text{First Switch Date}, \text{Last Contact Date}^*) - \text{Study Enrollment Date}) + 1]}{365.25}$$
- Consider events experienced up to First Switch Date (if switching from Initial Exposure) or whole study period (if no switch):
 
$$\text{Study Enrollment Date} \leq \text{Event Date} \leq \text{minimum}(\text{First Switch date}-1, \text{Last Contact Date}^*)$$
  - For incidence rate calculation only count new cases (i.e. first onset) of the event experienced during the period
  - For events rate calculation count all the events experienced during the period

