6.2 On Study Evaluations

After enrollment, patients will continue to be followed regardless of changes in medication until study completion. The investigator will manage the patient in accordance with their medical judgment and standard of care. Data will be collected on patients approximately every 6 months as outlined in the study calendar ([Table 6-1](#)). Each evaluation may be conducted within 2 months (± 2 months) of the scheduled data collection time point, except the last time point (Month 60), where data collection can occur up to +3 months.

The following data will be collected at each 6-month time point:

- SLICC/ACR Damage Index ([Appendix 5](#)).
- SLE medications (eg, immunosuppressants, BENLYSTA, antimalarials, corticosteroids, biologics, investigational agents for SLE). The name of each SLE medication and start and stop dates will be recorded. If a patient currently using BENLYSTA changes formulation, the original BENLYSTA record must be updated with a stop date and a new BENLYSTA record needs to be created with a start date for the new formulation. The new BENLYSTA record should also include formulation (IV or SC).
- In addition, the average daily dose of corticosteroids, in prednisone equivalents, will be recorded.
- Hospitalizations. Dates of inpatient hospital admission and discharge, and whether the hospitalization was SLE-related will be collected, as available.
- Adverse events of special interest (see [Section 7.2.1](#)). Note: In order to collect additional important information on potential suicidality-related events, should any of the events marked with an asterisk in [Appendix 2](#) occur, the investigator will be requested to complete the Possible Suicidality-Related History Questionnaire (PSRHQ) eCRF (only the first time a serious suicidality-related event is reported and a Possible Suicidality-Related Questionnaire (PSRQ) eCRF (each time a serious suicidality-related event is reported). The PSRHQ and PSRQ are provided in [Appendix 3](#) and [Appendix 4](#), respectively.

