8.1 General Statistical Considerations

This registry will observe mortality and AESI as well as effectiveness outcomes on patients with diverse treatment experience both during the registry and prior to enrollment. Some patients may enter the study already receiving BENLYSTA therapy (current user) and some patients may initiate BENLYSTA therapy within the last 2 months prior to study entry (treatment initiator). During the study, some patients receiving BENLYSTA therapy may stop and potentially restart therapy, and some comparison cohort patients may elect to initiate BENLYSTA therapy at some point subsequent to enrollment. Because of these complexities, a variety of analyses will be employed, some of which consider time periods of switching on and off BENLYSTA treatment. Since the initiation of this registry, a SC formulation of belimumab has been submitted for marketing authorization. The protocol database has been modified to capture formulation of BENLYSTA but reporting and analyses will not be separated by formulation.

Patients will be considered evaluable in the BENLYSTA cohort upon receiving a single, full or partial dose administration of BENLYSTA and collection of enrollment data (Section 6.1) and at least 1 post baseline assessment (Section 6.2). Patients will be considered evaluable in the comparison cohort if there is collection of enrollment data (Section 6.1) and at least 1 post baseline assessment (Section 6.2).

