## 5. CONSIDERATIONS FOR DATA ANALYSES AND DATA HANDLING CONVENTIONS

### 5.1. Study Exposure & Sub-group Display Descriptors

Exposure Group Descriptions			
Study Exposure Group		Data Displays for Reporting	
Code	Description	Description	Order in TLF
A	BENLYSTA	BENLYSTA	2
B	NON-BENLYSTA	NON-BENLYSTA	1

Exposure group comparisons will be displayed using the following specified descriptors:

- BENLYSTA vs NON-BENLYSTA

BENLYSTA group is used for subjects who are exposed to Benlysta while NON-BENLYSTA group is used for subjects who are not exposed to Benlysta. For summary description of baseline characteristics, the exposure group represents subjects' exposure at enrollment (i.e 'Initial Exposure'). For summary of safety and effectiveness endpoints, the exposure group will be defined using the 'Initial Exposure', 'As-Exposed', and/or 'Ever-Exposed' strategies (see Appendix 2, Section 9.2). 'As-Exposed' is defined based on whether or not a subject is using Benlysta at specific period during the study follow-up time; thus a subject's exposure group can change over time depending on switching to or off Benlysta. 'Ever-Exposed' is defined based on whether a subject was exposed to Benlysta at any point in time after enrollment, in this instance a subject's exposure can change only once over time if they were initially 'Unexposed' and then started using Benlysta; once a subject is exposed to Benlysta, they will always be considered as 'Exposed'.

The specific strategy for defining exposure group and the analysis approach for accrued data will be indicated on the TLFs titles and list of the planned data displays provided in Appendix 11 (Section 9.11).

---

 Subjects are considered to have switched from BENLYSTA exposure group if they permanently discontinued Benlysta treatment or missed doses of Benlysta for more than 98 days and do not restart doses of Benlysta on or before day 99 after the last Benlysta medication end date. Subjects are considered to have switched from NON-BENLYSTA exposure group if they initiate or start receiving Benlysta dose anytime during the study follow-up period. Change of different study-qualifying Non-Benlysta Standard of Care (SOC) medications does not count as exposure switching.

Primary analysis will be done on ‘Initial Exposure’ strategy for all endpoints while ‘As--Exposed’ and ‘Ever-Exposed’ will apply for some endpoints as exploratory analysis:

Endpoints	Primary analysis		Exploratory analysis	

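### While On Initial Exposure dates a true switch off BENLYSTA from the baseline record, which may have closed long before the drug was stopped

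*SAP*

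**What the plan says.** **The censoring date.** SAP 9.2.1.1, item 2, computes the First Switch Date of a BENLYSTA patient as "Baseline Benlysta Medication End Date" plus 98 days. The line carries a condition, "days (for switching from Benlysta to Non-Benlysta) or", and is followed by the corresponding rule for comparison patients (the day before their first post-baseline BENLYSTA start). The same hints keep all follow-up of a patient who never switches: "Consider events experienced up to First Switch Date (if switching from Initial Exposure) or whole study period (if no switch").

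**What counts as a switch.** The footnote to SAP 5.1 recognizes a switch off BENLYSTA only after a permanent stop or a dosing gap longer than 98 days. As a second condition, such patients must be ones who "do not restart doses of Benlysta on or before day 99 after the last Benlysta medication end date".

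**How records are kept.** Protocol 6.2 says that at a change between IV and SC "the original BENLYSTA record must be updated with a stop date and a new BENLYSTA record needs to be created with a start date". Footnote 4 to the schedule in SAP 9.1.1 repeats this.

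**What a baseline record is.** SAP 9.5.2 works record by record. A baseline medication starts on or before enrollment (or by Day 4) and is still running at enrollment. The section bridges one kind of gap: a BENLYSTA stop in the 98 days before enrollment with a restart within 98 days.

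**Role of formulation.** Protocol 8.1 says that "reporting and analyses will not be separated by formulation".

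**The concern.** The switch definition looks at the last BENLYSTA end date, but the formula that dates the switch looks at the baseline record. The two agree only when the baseline record is also the last record of the patient's first continuous BENLYSTA episode. A formulation change, or a stop and restart within the permitted gap, separates them.

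While On Initial Exposure is one of the two primary approaches in SAP 5.1 and one of only two that receive propensity weighting (Table 54.020). It is also used for hospitalizations. An early censoring date removes follow-up and events from the BENLYSTA arm alone, because record closure plays no part in the comparison arm's rule. What is removed is later time on drug, which a five-year safety registry is meant to observe.

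**Working it through.** **Step 1: which record does the formula point to?** A BENLYSTA record opened in, say, the second year starts after enrollment plus three days, so it cannot meet the SAP 9.5.2 definition of a baseline medication. Its end date is therefore not the baseline end date. The baseline end date is the day the earlier record was closed.

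**Step 2: does any rule join the records?**
- SAP 9.5.2 bridges only gaps that begin before enrollment. Where it does so there are two baseline records, and the SAP does not say which end date the formula means.
- SAP 9.5.3 combines multiple records only to compute exposure duration.
- SAP 9.2.1.2 (As-Exposed) uses a BENLYSTA end date without the word baseline, and likewise states no joining rule.
- In the SAP 9.2.2 table, subjects 3 and 6 have the same first BENLYSTA period under While On Initial Exposure and As-Exposed, so both strategies are meant to end it on the same date.

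**Step 3: worked dates.** These are illustrative: BENLYSTA at enrollment, last contact on day 1827 (the Month 60 target day in SAP 5.3).

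Formula as stated: baseline record end + 98. SAP 5.1 definition: end of last record before the true switch + 98, or last contact if there is no switch.

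| Patient | Formula as stated | SAP 5.1 definition | Lost |
|---|---|---|---|
| One record, stopped day 1000 | 1000 + 98 = 1098 | 1098 | 0 |
| IV closed day 365, SC at once, SC stopped day 1000 | 365 + 98 = 463 | 1000 + 98 = 1098 | 635 days |
| IV closed day 365, SC at once, never stopped | not applied (no switch) | 1827 | 0 |
| Closed day 365, restart day 425 (60-day gap), never stopped | not applied (no switch) | 1827 | 0 |

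For the second patient, 1098 − 463 = 635 days, and 635 / 365.25 = 1.74 years. This is 635 / 1098 = 58% of the time that should count. If the fourth patient later stopped on day 1000, the dates would be those of the second. In general the loss is the time from closure of the baseline record to the true stop, capped by last contact.

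**Step 4: scale.** The documents give no figure for this rule. The planned person-time reproduces: 2,000 × (1 − 0.9⁵) / (−ln 0.9) = 2,000 × 3.887 = 7,773 patient-years. The mortality half-width is 1.96 × √[0.0068 × (1/7,773 + 1/3,886)] × 100 = 0.318, which matches ±0.32 in Protocol Table 8-1.

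A ceiling on the years lost comes from assuming that a share of BENLYSTA patients has one closure, uniformly timed over five years, with 10% annual dropout, and that each loses everything from 98 days after the closure. The mean loss is 3.887 − 2.315 = 1.572 years per such patient. For a 30% share this is 2,000 × 0.30 × 1.572 = 943 patient-years, leaving 6,830, and the mortality half-width becomes 0.325. The actual loss for the same share is smaller, because only patients who later truly stop lose time, and only up to that stop plus 98 days.

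**The case against.** The strongest reply is that the SAP already protects most of these patients. A reader might infer that every patient who changes formulation or pauses briefly is censored 98 days later. The documents do not support that. The formula is limited to switches from BENLYSTA to Non-BENLYSTA, the hints keep the whole study period when there is no switch, and SAP 5.1 requires permanent discontinuation or more than 98 days of missed doses. SAP 9.2.2 runs the 98 days from cessation of BENLYSTA, and SAP 9.2.1.2 sets the number of exposure periods at switches plus one. This part of the reply stands in full, so cohort losses computed for all formulation changers are not the expected effect of the rule.

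A second reply is that the word medication may mean BENLYSTA as a whole, since the protocol defines it as any commercial formulation. A programmer who reads it that way gets the right date. This is possible, but the term is qualified by baseline, SAP 9.5.2 defines baseline by the start and end dates of each record, and no rule makes a later record part of the baseline one.

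A third reply is that the consequences are modest. Events and person-time are cut together, so neither the direction nor the size of any bias in a rate is shown. Precision barely moves, no hypothesis is tested, and ITT, which is also weighted, is untouched. SAP 9.2.1.1 also acknowledges that this approach uses only part of the follow-up. All of this stands. However, the acknowledged limitation is the loss of data after the first switch, whereas this defect removes data before it.

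**Conclusion.** The point holds in a narrow form. For a BENLYSTA patient whose baseline record closes at a formulation change or short interruption, and who later truly switches off, the stated formula gives a censoring date that contradicts the SAP's own switch definition. The loss per patient is the time between the two end dates: 635 days, or 1.74 years, in the example, with any events in that time. Only the BENLYSTA arm is affected.

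The conclusion rests on reading the baseline record as SAP 9.5.2 defines it. The number of affected patients is not in the documents and is left open. The case rests on a wrong date in a primary, propensity-weighted analysis, not on power or on a demonstrated bias. It should be corrected before the exposure dataset is final, but it does not undermine the registry's other analyses.

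**What to change.** In SAP 9.2.1.1, define the First Switch Date from BENLYSTA to Non-BENLYSTA as the end date of the last BENLYSTA record, of any formulation, in the continuous episode that includes the baseline record, plus 98 days. Join consecutive records whenever the gap between them does not meet the SAP 5.1 switch definition. Set no First Switch Date when no such switch occurs, and state that a formulation change is not a switch.

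Three related edits:
- Apply the same joining to the BENLYSTA end date in SAP 9.2.1.2 and check it against the 183-day window. A gap of more than 98 but not more than 183 days is a switch under SAP 5.1, yet BENLYSTA restarts before that window has run out.
- Correct the cross-reference in SAP 9.2.1.1 that reads as Section 5.14. Section 5.1 and its footnote are evidently meant.
- Reconcile the restart limit of day 99 in SAP 5.1 with the limit of 98 days between stop and restart in SAP 9.5.2. They agree only if the stop date is counted as day 1.

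The cost is a short SAP definition and a record-joining step in the exposure dataset. No new data are needed, and no treatment rule is involved.
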